1.2 Study Justification

Although community-based models of ART delivery have shown promising outcomes in relation to retention in care and adherence to treatment, (48) additional data is required from innovative community-based models of care to support long term retention as ART cohorts in resource limited settings continue to expand in the context of universal test and treatment. The lessons learnt will be needed to improve the efficacy and effectiveness of the HIV continuum of care and enable programs to redesign delivery systems and focus on less centralized treatment delivery points that often require

patients to travel long distances to health centre and also allow decentralization of health systems to meet scale-up targets and sustain treatment gains. Studies show that ART can be delivered through different routes but there is a lack of evidence about which model provides the most cost-effective strategy and how this can be integrated into other community-based programmes. This study will nest the evaluation of 2 different models of community ART delivery into an on-going cluster-randomised trial. The HPTN 071 (PopART) trial is currently evaluating the impact of community level combination prevention package, which includes universal HIV testing, active linkage to care and intensified provision of ART, on population level HIV incidence. This is a three-arm, cluster randomized, trial being implemented in 21 communities in of which 12 are in Zambia and 9 in South Africa. Arm A includes universal testing with immediate ART, Arm B includes universal testing with ART eligibility according to the current national guidelines and Arm C is the standard of care (control arm).

Fig 2. Schematic Diagram of the HPTN 071 trial

These interventions are being delivered by Community HIV Providers (CHiPs). The CHiPs are members of the community, appointed to provide a package of basic services at a household level, particularly HIV counselling and testing and linkage to care for those who are HIV positive. Their responsibilities include conducting HIV counselling and testing, condom distribution, screening for TB and linking household members for appropriate HIV prevention, treatment and care services. This study will utilise these existing community health care providers to implement 2 models of community-ART delivery:

1. CHiPs delivering ART packages to their clients on a regular basis
2. CHiPs facilitating Community ART clubs

It is not known whether these models of ART delivery will be feasible in urban low resource settings, or whether the care will be as good as the standard quality of care provided by the health systems, therefore this study is timely and innovative:

(1). This will be a first study in an urban setting in Zambia to rigorously evaluate different models of community ART delivery. This information will be critical for the continued scale up of universal test and treatment and may have cost efficient synergies utilising community HIV test providers.

(2). This study will be a randomized head to head non-inferiority comparison. To this date no studies have shown a comparison in clinical outcomes between the different Community ART models and between them and the current standard of care.

(3). This study will provide policy makers with evidence on operational feasibility, acceptability and cost effectiveness of two models and guide policy on the best models to roll out in the context of UTT.

The Zambian Ministry of Health has identified community models of ART delivery as a way of expanding treatment in the context of universal test and treat. The government, through the National AIDS Council, has engaged several in-country partners and researchers to pilot different community models of ART delivery in order to generate information required to inform model standardization at national level for wider roll-out. These models of care will only include stable adult ART patients, defined as patients on ART for more than 6 months who are virologically suppressed.

In addition to providing policy makers with evidence for community ART models, this study will also enhance the objectives of the HPTN071 trial where linkage to care and retention in care are essential for the outcome of the trial. This study will also increase local scientific capacity to conduct implementation research in order to sustain national ART and PEPFAR targets as well as build collaborations between indigenous Zambian non-profit organizations, the University of Zambia (UNZA) and Ministry of Health, drawing expertise that will ultimately strengthen Zambian research capabilities.

2.0 Study Objectives and Strategy

2.1 Hypothesis

Overall clinical, immunological and virological outcomes in patients receiving care via community ART delivery models are not inferior to those receiving care in the clinic (standard of care) in urban poor resource settings.

2.2 Primary Objective

To compare virological suppression at 12 months in HIV + patients receiving care via community ART models with those receiving care in the clinic (standard of care).

2.2.1 Secondary Objectives

1. To compare the proportion of patients with virological suppression at 24 months in patients receiving care via community ART models with those receiving care in the clinic (standard of care).

2. To compare Loss to Follow-up (LTFU) rates and missed dispensation of ARVs among individuals receiving care via community ART models with those receiving care in the clinic (standard of care), measured using routine health centre data

3. To compare HIV disease progression, and death among individuals receiving care via community ART models with those receiving care in the clinic (standard of care), measured using:

- CD4 cell count, WHO staging events, death from routine health centre data.

4. To qualitatively assess how health staff (including CHiPs) and PLWH on treatment experience the two models of care. This would be achieved through:

- Documenting treatment, adherence and retention experiences of PLWH accessing treatment through adherence club and home delivery models;

- Exploring the impact of the two models of care on access to treatment, adherence and retention according to the experience and perspectives of CHiPs and health facility staff;
- Qualitatively comparing how participant (PLWH and health staff) experience the models of care and experiences with the routine standard of care at the local health facilities;
- Qualitatively assessing participant (PLWH and health staff) perceptions about and experiences with the impact of the models of care on HIV services at the local health facilities.

5. To measure the health system costs of delivering the different community ART models.

In addition, we will measure the effect of the combined models on health facility crowding and waiting times as well as time to ART initiation of new patients in the 2 facilities (non- randomised comparison as both facilities have all models of care).

3.0 Methods

3.1 Study Design and Setting

The study will be a cluster-randomized non-inferiority trial in a prospective cohort of adults enrolled in to ART care at two urban primary health care facilities that serve two of the HPTN 071 trial communities in Lusaka, Zambia. These two communities include Chipata and Kanyama, which are the Lusaka arms A and B communities of the parent trial (HPTN 071) respectively. The reason for conducting the study in these two communities is that they are located in an urban setting where there is a high number of HIV patients in care, thus overburdening the clinics and an ideal setting to determine if these community models of ART delivery benefit the health care system in urban Zambia by decongesting clinics and making treatment easier to access.

The HPTN 071 (PopART) trial is evaluating the impact of community level combination prevention package, which includes universal HIV testing, active linkage to care and intensified provision of ART, on population level HIV incidence. This is a three-arm cluster randomized trial being implemented in 21 communities of which 12 are in Zambia and 9 in South Africa. These interventions are being delivered by Community HIV Providers (CHiPs) who are members of the community, appointed to provide a package of basic services at household level particularly HIV counselling and testing, linkage to care for those who are HIV infected, HIV/TB education, adherence support, distribution of condoms, screening household members for TB and STI and linking household members for appropriate HIV prevention, treatment and care services.

Before the start of the main trial, mapping of the households and non-residential buildings, with a census to count the number of adults (≥ 16 years old) and children (≤ 16 years old) was done and the map of the communities was created based on global positioning system (GPS) coordinates of all households and non-residential buildings. Following the mapping the data was used to define the catchment area of the clinic and to divide it into “CHiP zones” with one CHiP team being responsible for a zone. Each zone within these communities has approximately 400-450 households served by the CHiPs. Table 2 shows the number of CHiPs teams/zones in the 2 communities with the population each CHiP teams covers and the number of HIV positive adults being cared for in each zone

Table 2: Total number of zones in the communities served by the CHiP teams

	CHIPATA (54 Zones)			KANYAMA (50 Zones)		
	HIV+ clients	Total in care in the clinic	On ART in the clinic	HIV+ clients	Total in care in the clinic	On ART in the clinic
Average per zone	99.3	56	51.3	98.6	56.38	46.7
Range in the zone	33-234	14-155	18 - 143	48 - 213	4 - 143	3 - 102
Min-max						

Each zone is served by 2 CHiPs, therefore 1 CHiP will have an average of 23-25 clients on ART who may need to be provided with ART within the community.

3.1.1 Study Population

The eligible study population will include all stable HIV infected adult patients (≥ 18 years) on first-line ART residing in the 2 HPTN 071 communities and enrolled in the two primary health centres within the community. Stable patients are defined as those who are on first-line therapy, are on treatment and consistently retained in care for more than 6 months, virologically suppressed and have no other health conditions (e.g. TB, pregnancy and other opportunistic infections) requiring attention of a clinician.

3.1.2 Interventions

For this study, the two models of community ART will be either Adherence Clubs or Home Based ART Delivery.

A. Adherence Clubs

Adherence clubs will consist of a group of at least 20-25 stable patients who receive care from the community health care facility. Members of the club will meet every 3 months at an agreed communal venue where they will receive adherence support, symptom screening and pre-packed medications. Club members will be required to have 2 clinical/club visits (every 6 months) in a year for their routine clinical review and laboratory monitoring. The table below provides a broad overview of an ART Adherence Club.

Table 3. Broad overview of the ART Adherence club

Membership	
 1. Group of no more than 25 HIV positive stable patients 2. Should be residing in the clinic catchment area and accessing services within the facility
Club Meetings	Members will meet every third month (4 club meetings in a year – 2 at community level and 2 at facility level)
Clinic/Club Visits	Members will have a clinic visit once every 6 months Members will visit the clinic if the CHiPs refer them.
Process	
 1. During club meetings: 
 • Members will be assessed (symptom screen) • Adherence support • Group education and provision of condoms • Pre-packed drugs will be dispensed by the CHiPs 2. Clinical/Club visit 
 • Every 6 months the club visit will take place in the facility (either a particular afternoon or a weekend) • Clinical review by the clinician for all the club members • Routine laboratory monitoring for all the club members • Provision of pre packed drugs
Data collection	Data collected during the club meetings will be collected in a hand-held device integrated with current smart care system.

A common place within a particular zone will be identified as a club venue provided it is conducive for all members. These venues will be consistent and easily identified by the facility and club members. The club venues could be in schools, churches, communal clubs etc. and these can also change with time as long as this is agreeable with the club members and the health facility. In preparation of each club session, the facility in charge, CHiP supervisor and the CHiP should ensure that a few days prior to a club meeting:

- Club registers are reviewed to determine which club session will be taking place and in which community zone
- Identify and inform the CHiPs about the upcoming club meeting
- Collect members files from the facility registry and deliver to pharmacy for pre-packaging of drugs
- Send a reminder via phone call to members of their club meeting and venue.

The first club meeting will include registration and norms of the club. Thereafter, the first and successive club meetings will include:

- Club roster and registration of new members
- Updating contact details of all members
- Signing a charter of agreement about the club rules and norms
- Symptom screen checklist to determine if members have any symptoms
- Weight
- Group education on adherence and risk reduction counselling
- Dispensing the pre-pack medications upon receiving the prescription slip
- Distribution of condoms

For members who are symptomatic and show poor adherence, a referral slip will be given to them to refer to the clinician. During the club visits, all data will be entered into an electronic device that is programmed to refer a client back to the clinic if s/he has symptoms or abnormal findings.

At the end of the visit, members will be reminded of their next club meeting which will be indicated on their club card and their bi-annual clinic visits which will be indicated in their ART card.

If a member is absent during the club visit, this will be recorded in the register and the pre-packed drugs will be returned to the clinic. Attempts will be made to call the member to return to the clinic to collect his medicine from the pharmacy.

At the end of the club session, unissued pre-packed drugs will be returned to the pharmacy and registers will be updated before handing them over to the facility staff for ensuring completeness of the registers. All the data that was collected for each participant in the electronic device will then be synced with the clinic database.

Every 6 months, the club meeting will be conducted at the facility to coincide with their clinical review and laboratory monitoring. Club members will be informed to meet on a particular day and time at the health facility (this could be an afternoon during the weekdays or a Saturday morning as decided by the clinic staff). The club meeting will be conducted as above and in addition all members will be reviewed by the clinician and have their routine laboratory tests for monitoring. Drugs will also be pre-packed prior to this meeting and dispensed to the club members. A 1 x 3 monthly script will also be provided.

B. Home-Based ART Delivery

This model will provide ART care to clinically stable patients in their homes. The CHiPs will visit the participant's homes once every 3 months to provide adherence support, symptom screening and dispense pre-packed drugs to the participant. The participant will only be required to visit the clinic twice in a year for routine clinical review and laboratory monitoring. The table below provides a broad overview of the home-based ART delivery model.

Table 4: Broad Overview of the Home-Based ART delivery model.

Membership	
 1. Should be residing in the clinic catchment area and accessing services within the facility 2. Clinical stable patient 3. Can include 1-2 members of the same household
Home visits	Clients will be visited once every 3 months at their homes
Clinic Visits	
Clients will have a clinic visit once every 6 months
 
Clients will visit the clinic if the CHiPs refer them.

Process	
 1. During home visits: 
 • Clients will be assessed (symptom screen) • Adherence support provided • Health education and provision of condoms • Pre-packed drugs will be dispensed 2. Clinical visit – every 6 months 
 • Clinical review by the clinician • Routine laboratory monitoring • Provision of drug scripts • Drug dispensation
Data collection	Data collected during the home visits will be collected in a hand-held device integrated with current smart care system.

The client's physical address and contact details will be entered in a home-based register, which will be updated at every home visit to ensure contact with the client, is maintained. Home and clinic visit dates will be provided to the client at each visit and clients will also be reminded they will be called at least two days prior to their home visit to schedule the appropriate visit times.

Once a client has been enrolled into home based ART delivery model, the client will be provided with 3 monthly prescription slips for the current drug regimen they are on. On the day of registration into the model of care, the client will be required to collect a 3 months prescription of drugs to last before the first home visit. The facility nurse will ensure that the client has been provided with 1x3 monthly scripts.

All clients receiving home-based ART service will be recorded in a register for use at the facility and their clinic folders will be kept in a separate filing cabinet specific for home based ART delivery.

It will be the responsibility of the facility, CHiP supervisor and the CHiP to review the registers on a weekly basis to determine the number of home visits scheduled for the week. 2-3 days prior to a home visit, the Facility-in-charge and the CHiPs supervisor should ensure:

- Registers are reviewed to see where home visits will take place and in which zone
- Identify and inform the CHiPs about the upcoming home visits and the physical address
- Collect members files from the registry and deliver to pharmacy for pre-packaging of the drugs
- Notify members of their upcoming visits

The first home visit will include registration and norms of the visits. Thereafter, the first and successive home visits will include the following:

- Updating contact details in the register
- Weighing of client
- Symptom screen checklist
- Health education on adherence and risk reduction counselling
- Dispensing pre-packed drugs and condoms
- Date of next visit
- Reminding clients of their bi-annual clinical visit
- Refer clients who are symptomatic

For participant's who are symptomatic and show poor adherence, a referral slip will be given to them to refer to the clinician. During the home visits, all data will be entered into an electronic device that is programmed to refer a client back to the clinic if s/he has symptoms or abnormal findings.

At the end of the visit, client will be reminded of the next home visit and clinic visit. These reminders will be indicated on their home visit and ART cards.

If a participant is not found at home during the visit, s/he will be called or anyone present at home will be given the message to ask the client to return to clinic to collect drugs. If a participant is contacted and agrees to schedule a home visit within 7 days of the missed visit, then the CHiP will reschedule the visit. This will be recorded in the register as missed visit and the pre-packed drugs will be returned to the clinic. Should a client continue to be absent during home visits on more than 2 scheduled home visits, s/he will be followed up and transitioned to mainstream care.

In a household where a couple or two members are both part of this models of care, and one member is absent, all efforts must be made to ensure the absent member is followed up for another unscheduled visit.

All the data that was collected for each participant in the electronic device will then be synced with the clinic database.

Every 6 months, the client will be required to visit the health facility for their clinical review and laboratory monitoring. In addition they will be given a 3-monthly drug supply and provided with a 1x3 monthly drug script. All clients in home based care will be required to visit the facility on a certain day to ensure that they are fast tracked and received their pre-packed drugs within the facility.

SCHEDULE OF VISITS FOR BOTH ADHERENCE CLUBS AND HOME-BASED DELIVERY

Stable patients in both models of care will follow the visit schedule below:

1. Home or club visits every 3 months (depending on the models of care)
2. Clinical visit every 6 months

Clinic visit for enrolment	1 st visit	2 nd Visit at the Clinic	3 rd visit	4 th visit at Clinic
0 month	Month 3	Month 6	Month 9	Month 12
Clinic Level	Community Level	Clinic level	Community Level	Clinic level
Enrolment into club or home based visit	Introductory and standard session in both clubs and home based care	1. Adherence Clubs: Meet at the facility on a particular day or weekend	Standard session Review of results	Same procedure as in month 6
Norms of the models of ART delivery	Adherence support	Conduct the usual club meeting at the facility	Adherence support	
3-month drug supply	Symptom screening Dispense 3-monthly pre-packed drugs	Clinical and laboratory review 3 months pre-packed drugs provided 1x3 month drug script issued	Symptom screening Dispense 3-monthly pre-packed drug	
		2. Home Based ART Delivery Clients in this model meet at the clinic on a particular day or weekend. Adherence support by the CHiPs Clinical review and Laboratory Monitoring Pre-packed drugs dispensed Issuing of 1x3 month drug script		

CLINICAL MANAGEMENT OF CLIENTS IN BOTH MODELS OF CARE

Clients in both models of care will need to be followed up closely to ensure that they are stable and this will be done every 6 months at the facility. The 6 month clinical visit will ensure clients receive a complete clinical review and routine laboratory tests are conducted. When a client is reviewed by the clinician, it will be the clinician's decision to determine if s/he remains as part of the community models of care or return to mainstream care. The criteria for returning to mainstream care include:

1. Presence of an opportunistic infection (TB)
2. Detectable viral load
3. Routine blood results significantly abnormal
4. Poor adherence to home visits
5. Patient request
6. Patient has moved out of the community zone where home-based ART delivery services are not available

Members who belong to the adherence club will be informed that this particular club session will take place in the clinic where the Health care workers will conduct a clinical review and laboratory monitoring. The standard session of the clubs will also take place during this time and pre-packed

drugs will be dispensed to them. In order to expedite this club session, the health care workers and club members will agree on a particular day and time when to have the session every 6 months.

For clients in the home based ART model, they will also be expected to visit the clinic every 6 months on a particular day or weekend where their clinical review and laboratory monitoring is fast tracked by the community ART nurse. 3 monthly pre-packed drugs will also be provided.

Once a client has had his clinical visit, the club and home ART register will be updated as having had a clinical visit and laboratory results will also be updated.

If a client has abnormal lab results, s/he will be called to the clinic for review by the clinician.

All laboratory results should be reviewed by the Facility ART in charge and any abnormal results should be discussed with the clinician and the research team. Management of such clients will be according to standard practice.

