- Proportion of patients with continuous immunologic/virologic suppression
- Proportion of patients who develop opportunistic infections in the models of care
- Transition rates of newly eligible patients into the community models
- Transition rates of patients from community models back to facility care

Data Security

Data will be securely stored according to Ministry of Health and Smart Care guidelines that are already in place for all health care centres providing HIV care. All CHiPs involved in community of ART model delivery will have to sign a consent form as per smart care National Guidelines which explicitly explains data confidentiality and respect of clients. Data captured electronically in the device is encrypted and once it is synced with the health centre database, protected by Microsoft SQL security. Access of all data in the health centre database will be based on user right and every user in the facility has to agree to terms of use, which is currently in place. The Audit Trail in Smart Care that is currently in place in all ART health centres logs key events, which occur in the system. It logs information such as who logged into the system, which patient reports they run, changes to inventory and who created a back up. Every single interaction has the identifier of whoever entered the data as well. This trail will be used for security and audit purposes.

In order to obtain the data for monitoring and evaluation as well as for research purposes both by implementing partners and Zambart research teams, permission will be sought from the Ministry of Health. The study team will then periodically extract this data for measuring the outcomes of the study.

Investigators will also allow inspection of all study-related documentation by authorized representatives of the HPTN LOC, SDMC, LC, NIAID, US and in-country government and regulatory authorities and IRBs/ECs. A site visit log will also be maintained at the study site to document all visits.

Qualitative Data Collection

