8.3 Anticipated Risks

Researchers recognize the fact that there might be breach of confidentiality among health workers and CHiPs as a result of the study. The interaction of the CHiPs and research staff with various health workers within the study sites may disclose participant's personal and confidential information to

researchers. For this reason, all research staff will receive good clinical practice/research ethics training at the beginning of the study. All research staff and CHiPs will be counselled to observe maximum confidentiality of any information revealed to them during and after the study.

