8.4 Benefits to the Study Participants

There will be no direct and immediate benefit in terms of monetary and/or material benefit during and/or at the end of the study. For this reason the participants will be well informed that their participation is purely voluntary and that they have the right to withdraw at any time.

Benefits anticipated to the participants include less frequent travel to the clinics for their pharmacy refill; reduce waiting time and privacy within the clubs and their homes.

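### After a missed home visit, a drug-collection message may be left with anyone in the house; this can reveal HIV treatment by inference and is in tension with the confidentiality commitment in Section 8.3

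*Protocol*

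**What the plan says.** Protocol Section 3.1.2, part B, covers the home-delivery participant who is not found at the scheduled visit: "s/he will be called or anyone present at home will be given the message". The second option reads in full: "anyone present at home will be given the message to ask the client to return to clinic to collect drugs". If the participant is contacted and agrees to a new date within 7 days, the visit is rescheduled.

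Other parts of the protocol bear on this sentence:

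- Section 8.3 (Anticipated Risks) says that research staff and CHiPs will be "counselled to observe maximum confidentiality of any information revealed to them during and after the study". It recognises that "there might be breach of confidentiality among health workers and CHiPs as a result of the study".
- Section 5.0 (Data Security) has CHiPs sign a form that "explicitly explains data confidentiality and respect of clients".
- Section 8.4 gives among the anticipated benefits "reduce waiting time and privacy within the clubs and their homes", evidently meaning privacy as a gain.
- Section 3.1.2, part A, deals with a member absent from an adherence club. The member is telephoned; nobody else is given a message.

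**The concern.** The sentence in part B does not limit who may take the message. It does not ask for a nominated person, an adult, a household member, or someone who already knows the participant's HIV status. A visitor or a child would qualify. It does not require the call to be tried before a message is left. It also fixes the content, clinic and drugs, where a bare request to get in touch would serve the same purpose.

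The person who leaves the message is a Community HIV Provider drawn from the same community. Sections 1.2 and 3.1 describe the role mainly in terms of HIV counselling, testing and linkage to care. A listener who knows this can work out what the drugs are for. What is at stake is involuntary disclosure of HIV treatment, which cannot be undone and which could result from following the protocol exactly.

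**Working it through.** No arithmetic applies and the protocol gives no figure to reproduce. The check sets the texts side by side.

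1. **Who may be told.** Part B permits whoever is at home. The eligibility criteria (Section 3.1.3) ask for written consent and acceptance of the CHiP intervention. They do not ask that the participant has disclosed at home, so people who have not disclosed can be enrolled and can choose home delivery.

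2. **What is told.** The message mentions the clinic and drugs, but not HIV or ART. Any disclosure is therefore by inference from two things together: the messenger's role and the content.

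3. **Who speaks.** The CHiP's title contains HIV and the CHiP is local. Section 3.1 also lists TB and STI screening, condom distribution and linkage to other services. A CHiP at the door does not by itself mark a household. A CHiP telling a third party that a named person must collect drugs is more specific than that.

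4. **Against Section 8.3.** CHiPs are to keep maximum confidentiality about anything revealed to them. That a named person has drugs waiting at the clinic is information held through the study. A CHiP who gives it to an unselected third party is following part B and falling short of the standard in 8.3. The two texts can be reconciled, but they have not been.

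5. **Against the risk that 8.3 names.** The route it spells out runs through contact between CHiPs, research staff and health workers. Household members and visitors are not mentioned.

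6. **Against the club procedure.** Both community models must reach someone who missed a dispensing contact. Part A does so with a call to the member alone; part B adds the open third-party message. The exposure thus belongs to the home-delivery arm (35 of 104 zones in Section 3.1.4).

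7. **Whether the means for a tighter rule exist.** Part B already keeps a home-based register with address and contact details, updated at every visit, and already has clients called at least two days ahead to arrange a time. An agreed contact route fits into that register.

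**The case against.** The best case for leaving the text alone has five parts.

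- **The message is one of two options.** The participant may be called instead. This is correct, and it would be wrong to say that CHiPs are simply instructed to leave word with anyone. The third-party route is still authorised without condition or order of preference.
- **Unexpected absence should be uncommon.** Calls before the visit and updated contact details make it less likely. This stands, but it reduces how often the sentence applies and does not change what it permits.
- **The message does not name HIV, and CHiPs offer other services.** This also stands. It makes disclosure possible and not certain, and it makes the conflict with 8.3 a tension and not a flat contradiction.
- **The participant chose home delivery and may leave it at any time.** That choice accepts CHiP visits at times arranged with the participant. It does not obviously accept messages through whoever answers the door. The consent form was not in the reviewed text and may cover household contact, so it cannot be said that permission is missing.
- **A message may be the only way to reach someone without a working phone.** This is a fair point, and the fix should keep a fallback.

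Two stronger readings are tempting and should not be drawn. A reader might infer a count of disclosures per year, but the documents give no absence rate, no uptake of home delivery and no split between calls and messages. A reader might also infer that the message biases results in Arm 2. No text links it to refusal, switching or missed refills; refusal at baseline comes before any missed visit; and the missed-visit procedure is part of the model being tested.

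**Conclusion.** The point holds as a matter of participant protection. Part B of Section 3.1.2 permits an unrestricted third-party message with revealing content, as an unranked alternative to calling the participant. It can disclose HIV treatment by inference, it is in tension with Section 8.3, and it is looser than the club procedure in the same section.

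No size can be put on it from the documents. No endpoint, non-inferiority margin, sample size or power figure is affected. The conclusion rests on one assumption: that people in these communities recognise CHiPs as HIV providers, which their title and listed duties support. The correction is worth making because it is cheap and the possible harm is irreversible.

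**What to change.** Reconcile the missed-visit sentence in Section 3.1.2, part B, with Section 8.3:

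1. At enrolment, record in the home-based register, with the contact details already kept there, the participant's agreed contact route and any named person who may take a message.
2. When the participant is out, try the call first. Leave a message only with the named person. With anyone else, leave at most a neutral request to contact the CHiP that mentions neither the clinic nor drugs.
3. In Section 8.3, name disclosure to household members or visitors as a risk, and keep the wording consistent with the consent form.

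The cost is one register field, one reworded procedure, a line in 8.3 and a short addition to CHiP training. The drawback is that some participants who cannot be phoned and have named nobody may be reached later or with more effort. The neutral request keeps a fallback for them. No visit schedule, dispensing rule or criterion for return to mainstream care needs to change.
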